Subjects in Arm 1 will be required to visit the Bilaspur ICC once weekly for four weeks. During these visits, participants in Arm 1 will receive their pegylated interferon alfa-2a shots subcutaneously at the clinic by a registered medical practitioner. They will be compensated INR 100 (USD 1.5) for these visits (since this is not the standard of care).

Subjects in Arms 1 and 2 will also receive 3 doses of SOF and DAC, which they will be instructed to take home and use as backup in case there is a problem receiving the daily medication from field workers. Otherwise, all doses of SOF and DAC will be delivered as directly observed therapy (DOT) daily in the field including Saturday and Sunday doses. Peer-health workers (PHW) (1 per 15-20 participants: total 4 for the study) will deliver the SOF and DAC via DOT on a daily basis to a location of the participant's choosing. We will provide the PHW with laptops/tablets that have a fingerprint reader to record the daily delivery of SOF and DAC and also to also ensure that the drugs are being delivered to the correct participant.

Subjects in Arm 3 will receive their first 4 weeks of treatment supply at baseline and two refills of 28 day's worth of doses at Weeks 4 and 8.

Dose Reduction

If a serious adverse reaction develops in Arm 1 participants during the course of treatment (See Section 8c), the dose of PEG will be modified according to standard guidelines until the AE abates or decreases in severity. See Table 1 for procedures related to depression and see Table 2 for procedures related to hematologic abnormalities. Selective serotonin reuptake inhibitors are available through government hospitals in India and will be made available to study subjects as needed. If persistent or recurrent serious adverse events develop despite adequate dosage adjustment, treatment will be discontinued.

Table 1. Procedures for Dose modification for serious adverse events related to depression

Depression Severity	Initial Management (4-8 weeks)		Depression		
	Dose modification	Visit Schedule	Remains stable	Improves	Worsens
Mild	No change	Evaluate once weekly by clinician at visit and daily recording of symptoms by outreach worker in field	Continue weekly visit schedule	Continue weekly visit schedule	(See moderate or severe depression)

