Moderate	Decrease PEG dose 50%	Evaluate once weekly by clinician at visit and daily recording of symptoms by outreach worker in field	Consider psychiatric consultation. Continue reduced dosing.	If symptoms improve and are stable for 4 weeks, may resume normal visit schedule. Continue reduced dosing or return to normal dose.	(See severe depression)
Severe	Discontinue PEG permanently	Immediate psychiatric consult with CIMS	Psychiatric therapy as necessary as supervised by physician at CIMS		

Table 2. Procedures for Dose modification for serious adverse events related to hematologic abnormalities

Laboratory values		Pegylated Interferon $\alpha 2a$
Hgb	<10.0 g/ dl	---
	<8.5 g/dl	Permanently discontinue
WBC	<1.5 x 10 ⁹ /L	Reduce dose by 50%
	<1.0 x 10 ⁹ /L	Permanently discontinue
Neutrophil	<0.75 x 10 ⁹ /L	Reduce dose by 50%
	<0.5 x 10 ⁹ /L	Permanently discontinue
Platelets	<50 x 10 ⁹ /L	Reduce dose by 50%
	<25 x 10 ⁹ /L	Permanently discontinue
Bilirubin – direct	2.5 x ULN*	Permanently discontinue
Bilirubin – indirect	>5 mg/dl	
	>4 mg/dl (for 4 weeks)	Permanently discontinue
Creatinine	> 2 mg/dl	Permanently discontinue
ALT/AST	2 x baseline and 10 x ULN	Permanently discontinue

*ULN = upper limit of normal

Treatment interruption

We will track missed doses using our biometric system in Arms 1 and 2. Participants who miss ≥ 1 but fewer than 2 weeks of doses will have their treatment extended so that they complete the total number of doses in their assigned arm (e.g., 28 for Arm 1 and 84 for Arm 2). If a client misses 2 weeks or more of therapy,

treatment will be restarted in its entirety at the discretion of the study physician and in consultation with the participant. Treatment can only be restarted one time. If there is a second interruption of >2 weeks, treatment will not be restarted. Participants in Arm 3 will be counseled to complete all doses of medications even if it takes longer than 84 days (e.g., 94 days). If participants in Arm 3 report an interruption >2 weeks at their 4-weekly medication refill visit, they will also be provided with one opportunity to restart treatment for the entire duration of 12 weeks at the discretion of the study clinician as with Arms 1 and 2.

4a5.3. End of Treatment Visit

The following procedures/assessments will be completed at the End of Treatment Visit

- Obtain vital signs
- Assessment of adverse events and concomitant medications

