- Review medication compliance with subject. Subject should bring any missed doses to this visit.
- Obtain blood samples for sample storage in Table 3
- Brief survey on quality of life and alcohol and drug use
- Perform targeted physical examination
- Chart review of YRG-JHU ICC data to document HIV and antiretroviral therapy status and engagement in opioid substitution therapy (OST)

4a5.4. Early termination visit

Subjects discontinuing treatment prior to completion of the assigned dosing period will be asked to complete an Early Termination visit as described below. In addition, these subjects will be asked to complete the 12-week Post Treatment visit. Subjects with HCV RNA < lower limit of quantification (LLOQ) who permanently discontinue all study drugs for any reason including safety and/or tolerability concerns prior to completion of the assigned dosing period will be followed according to the post-treatment study assessments to determine whether the subject achieves SVR.

The Principal Investigator will be consulted prior to subject discontinuation when medically feasible. Study medication will be discontinued in the follow instances:

- Unacceptable toxicity, as defined in Section 8c of the protocol, or toxicity that, in the judgment of the study clinician and principal investigator, compromises the ability to continue study-specific procedures or is considered to not be in the subject's best interest
- Pregnancy in female participants
- Significant protocol violation including non-compliance with study assessments
- Subject requests to discontinue for any reason

The following procedures will be performed at the early termination visit.

- Perform targeted physical examination
- Obtain vital signs
- Obtain body weight
- Assessment of adverse events and concomitant medications
- Obtain blood samples for:
 - HCV RNA testing
 - Complete blood count
 - Liver function tests
 - Renal function tests
 - These samples will be used to estimate FIB-4 (stage fibrosis)
- Brief survey on quality of life and alcohol and drug use
- Subject should return all extra medication doses at this visit
- Chart review of YRG-JHU ICC data to document HIV and antiretroviral therapy status and engagement in opioid substitution therapy (OST)

4a5.5. 12-week post-treatment visit (Week 16 for Arm 1 and Week 24 for Arms 2 and 3)

The following procedures will be performed at the 12-week post treatment visit.

- Obtain vital signs
- Obtain body weight

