Peglyated-interferon alfa-2a is commercially available as Taspiance by Emcure Pharmaceuticals in India and will be provided in this study as 180 µg/0.5 mL pre-filled syringes. Each syringe is to deliver 0.5 mL of drug product. The formulation, which is subcutaneously administered, contains sodium chloride, polysorbate 80, benzyl alcohol, sodium acetate trihydrate, acetic acid, and water for injection. The solution is colorless to light yellow and the pH is 6.0 ± 0.5.

Packaging and Labeling

The PEG will meet all applicable requirements of Good Manufacturing Practices: Manufacture of

investigational medicinal products (July 2003) and the Drug Controller General India (DCGI).

Storage and Handling

Peglyated-interferon alfa-2a prefilled syringes will be stored in the refrigerator at 2 °C to 8 °C (36 °F to 46 °F) protected from light and will not be frozen or shaken. Syringes are for single use only.

b. Justification and safety information if FDA approved drugs will be administered for non-FDA approved indications or if doses or routes of administration or participant populations are changed.

N/A

c. Justification and safety information if non-FDA approved drugs without an IND will be administered.

N/A

7. Study Statistics

a. Primary outcome variable.

The primary outcome will be sustained virologic response (SVR12), which is defined as HCV RNA < lower limit of quantification 12 weeks after treatment completion.

b. Secondary outcome variables.

Adherence for comparison across the three arms will be defined using a combination of the biometric data for Arms 1 and 2 and self-report and pill counts for Arm 3. Serious adverse events requiring dose modification or treatment discontinuation will include primarily laboratory abnormalities including anemia, neutropenia and thrombocytopenia. For any adverse event outcome, we will consider occurrence of any of the side effects commonly associated with treatment with pegylated interferon alfa-2a, including but not limited to fatigue, headache, pyrexia, myalgia, rigors, insomnia, nausea, alopecia, irritability, arthralgia, anorexia, dermatitis, depression, or fatigue.

c. Statistical plan including sample size justification and interim data analysis.

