All analyses will be conducted as intention to treat. We will use a chi-squared test of proportions to compare the proportions that achieve SVR12. Pairwise comparisons with correction for multiple comparisons will be conducted to directly compare Arms 1 and 2, Arms 1 and 3 and Arms 2 and 3. For secondary outcomes, chi squared tests of proportions will be used to compare categorical outcomes and a Wilcoxon rank-sum test will be used to compare adherence.

The primary objective of this study is to test the feasibility of DOT for HCV treatment among HCV-infected persons with substance use history in a resource limited setting. An additional objective is to generate pilot data to plan a larger powered study. We hypothesize that SVR12 will be higher in Arm 1 compared to Arms 2 and 3. Assuming a two-sided $\alpha=0.05$, 50 people in each arm and 70% achieving SVR12 in Arm 3, we will have >80% power to detect a difference of 25% (e.g., 95% completion in the SOF+DAC+PEG).

No interim analyses will be conducted as with 150 participants, it will not be possible to observe statistical differences prior to the completion of the trial.

d. Early stopping rules.

As we do not plan to do interim analyses, the only reason for stopping the trial would be a higher frequency than expected of serious adverse events. We will continually monitor the frequency of serious adverse events and if this frequency is 10% or higher, we will prematurely stop the trial.

8. Risks

a. Medical risks, listing all procedures, their major and minor risks and expected frequency.

It is anticipated that most participants who complete their full course of treatment with optimal adherence will clear hepatitis C from their bodies. However, for those individuals who do not respond to treatment, it is possible that non-response will affect their ability to respond to other drugs for hepatitis C in the future. However, with the newer direct acting antiviral (DAA) regimens, response rates have been demonstrated to be comparable in treatment naïve and prior non-responders. The primary risk related to taking these medications is with respect to side effects associated with pegylated interferon alfa2a.

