- Persistent or significant disability/incapacity
- Congenital anomaly/birth defect in the offspring of a subject who received investigational medicinal product
- Other medically significant events that may not be immediately life-threatening or result in death or hospitalization, but based upon appropriate medical and scientific judgement, may jeopardize the subject or may require medical or surgical intervention to prevent one of the outcomes listed above

Examples of such events are as follows:

- Intensive treatment in an emergency room or at home for an allergic bronchospasm
- Blood dyscrasias or convulsions that do not result in hospitalization
- Development of drug dependency or drug abuse

8c2.1. Classification of Serious Adverse Events (SAEs)

- Death is an outcome of an AE, and not an adverse event in itself. In reports of death due to “Disease Progression,” where no other information is provided, the death will be assumed to have resulted from progression of the disease being treated with the study drug.
- The subject may not have been on the study drug at the occurrence of the event. Dosing may have been given as treatment cycles or interrupted temporarily before the onset of the SAE, but may have contributed to the event.
- “Life-threatening” means that the subject was at immediate risk of death from the event as it occurred. This does not include an event that might have led to death if it had occurred with greater severity.
- Complications that occur during hospitalizations are AEs. If a complication prolongs the hospitalization, it is an SAE.
- “In-patient hospitalization” means the subject has been formally admitted to a hospital for medical reasons, for any length of time. This may or may not be overnight. It does not include presentation and care within an emergency department.
- The investigator should attempt to establish a diagnosis of the event on the basis of signs, symptoms and/or other clinical information. In such cases, the diagnosis should be documented as the AE and/or SAE and not the individual signs/symptoms.

A distinction should be drawn between the seriousness and the severity of the AEs. An AE that is assessed as Grade 4 (potentially life-threatening) should not be confused with an SAE. Severity is a category utilized for rating the intensity of an event; and both AEs and SAEs can be assessed as Grade 4. An event is defined as “serious” when it meets one of the predefined outcomes described above.

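### The protocol uses *serious* in two incompatible senses, and the PEG dose trigger, the SAE outcome and the stopping rule depend on which one applies

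*Combined protocol and SAP*

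**What the plan says.** - **Trigger (Dose Reduction paragraph of 4a5.2).** "If a serious adverse reaction develops in Arm 1 participants during the course of treatment (See Section 8c), the dose of PEG will be modified". The same paragraph sends staff to Table 1 for depression and to Table 2 for hematologic abnormalities. It adds that treatment stops if serious events persist or recur after the dose has been adjusted.
- **Table 1.** The title is "Table 1. Procedures for Dose modification for serious adverse events related to depression". Its rows are severity grades. The Mild row carries no dose change and, on worsening, refers on: "See moderate or severe depression". The Moderate row orders a cut of half ("Decrease PEG dose 50" per cent) and keeps the reduced dose while the depression is stable.
- **Table 2.** It is also titled as covering serious adverse events. Its rows are laboratory cut-offs, including bilirubin, creatinine and ALT/AST.
- **Secondary outcome (7b).** "Serious adverse events requiring dose modification or treatment discontinuation will include primarily laboratory abnormalities including anemia, neutropenia and thrombocytopenia". Depression appears in 7b under any adverse event, not under SAEs.
- **Definition (8c2 and 8c2.1).** Serious means one of a list of outcomes, including a clause for medically significant events that rests on judgment. One example given for that clause is a blood dyscrasia without hospital admission. Section 8c2.1 adds: "A distinction should be drawn between the seriousness and the severity of the AEs". All SAEs go to both IRBs within 24 hours.
- **Stopping rule (7d).** SAE frequency is monitored continually, and "if this frequency is 10% or higher, we will prematurely stop the trial".
- **Early termination (4a5.4).** One ground for stopping study drug is "Unacceptable toxicity, as defined in Section 8c of the protocol".

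**The concern.** One word carries four functions: it starts a PEG dose change, defines a secondary outcome, sets the 24-hour reporting duty and feeds the only rule that can stop the trial. Section 8c gives it an outcome-based meaning. The two table titles and 7b give it a meaning based on severity grades and laboratory values. Two careful people at the site could therefore classify the same event differently and each cite the protocol.

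The tables govern PEG, which only Arm 1 receives. In an unblinded three-arm safety comparison, any event that becomes an SAE only because a table title calls it one is added to Arm 1 alone. The SAE contrast between arms would then partly reflect the definition chosen.

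**Working it through.** The 10% in 7d is stated without derivation, so there is no planned figure to reproduce. The check is mainly a comparison of texts.

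**Step 1. Apply each sense of *serious* to the same Arm 1 event.**

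| Event | What the table orders | Serious under 8c2? | Result |
|---|---|---|---|
| Moderate depression, no admission | PEG dose halved | No listed outcome is evident | Table acts; 4a5.2 trigger not clearly met |
| Direct bilirubin, creatinine or ALT/AST past its cut-off | Permanent discontinuation of PEG | No listed outcome is evident from the value alone; not a blood dyscrasia | Same conflict |
| Neutrophils 0.6 x 10^9/L (between the 0.5 and 0.75 cut-offs) | PEG dose halved | Possibly, through the judgment clause and the blood dyscrasia example | Left to case-by-case judgment |
| Mild depression | No dose change | No | An SAE only by the Table 1 title |
| Hemoglobin below 10.0 but not below 8.5 g/dl | No dose entry | Not from the value alone | An SAE only by the Table 2 title; women may enroll at 9 g/dl (Section 5) and so already be in this row |

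The first two rows are the clear conflict. The third is ambiguous. The last two affect counting only, not dosing.

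**Step 2. Check the discontinuation sentence against Table 1.** Take moderate depression that stays stable after the PEG reduction. If the table title is read literally, this is a persisting SAE after dose adjustment, and 4a5.2 stops treatment. Table 1 continues the reduced dose. If 8c2 is applied instead, the stop sentence is not met, but neither is the trigger for the reduction that Table 1 ordered. Neither sense makes the section consistent.

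**Step 3. Check the 4a5.4 pointer.** Section 8c covers AE and SAE definitions, causality, grading and reporting. It does not define unacceptable toxicity.

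**Step 4. See whether the count could matter for 7d.** The rule names no denominator. Ten per cent is 0.10 x 150 = 15 participants overall, or 0.10 x 50 = 5 if Arm 1 alone is meant. The documents give no rates for Table 1 or Table 2 events, so the Arm 1 rate q below is an assumption. With no SAEs in Arms 2 and 3 and full enrolment, the chance of reaching a threshold r is the sum over k from r to 50 of C(50,k) q^k (1-q)^(50-k).

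| Assumed q | At least 15 of 150 | At least 5 of 50 (Arm 1) |
|---|---|---|
| 5% | <0.001 | 0.104 |
| 10% | <0.001 | 0.569 |
| 20% | 0.061 | 0.982 |
| 30% | 0.553 | >0.999 |
| 40% | 0.946 | >0.999 |

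If 2% of participants in Arms 2 and 3 also have an SAE, the overall figures at q = 20% and 30% become 0.210 and 0.757. Continual monitoring can only raise these chances, since one event among the first ten participants is already 10%.

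**Step 5. Limit on step 4.** Table 3 places CBC, LFT and RFT at Screening and SVR12 only. Apart from unscheduled tests or an early termination visit, laboratory events during four weeks of PEG would go unseen, so observed counts could be well below the assumed rates. Depression is less limited in this way: Table 1 provides weekly clinician evaluation and daily field recording for mild and moderate cases.

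**The case against.** The strongest reply is that this is loose wording which staff would read sensibly. Section 4a5.2 points directly to the tables, each row carries its own threshold, and the trigger sentence also refers to standard guidelines. The 8c2 judgment clause, with its blood dyscrasia example, can cover the anemia, neutropenia and thrombocytopenia named in 7b. Section 4a5.4 allows stopping on the judgment of the clinician and principal investigator, which limits the harm from the broken pointer. The earlier pilot reported no serious adverse events with 12 weeks of PEG, although its SAE definition is not given.

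Much of this stands, and it rules out several stronger readings that a reader might infer:

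- That the tables are blocked. The direct pointer to them makes this unrealistic.
- That a strict reading empties the 7b outcome. Some cytopenias can qualify under 8c2.
- That 7b makes depression an SAE. It lists depression under any adverse event; only the Table 1 title suggests otherwise.
- That routine laboratory changes will stop the trial. The Table 2 rows that change the dose are marked abnormalities, no rates are given, and no on-treatment laboratory tests are scheduled. With all 150 as denominator and no SAEs elsewhere, even a 20% Arm 1 rate reaches the threshold with a chance of only 0.061.

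The reply does not reach moderate depression, the non-hematologic rows, the clash over discontinuation or the question of which events 7b and 7d count. Discretion to discontinue does not settle any of these.

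**Conclusion.** The concern holds as an internal contradiction in the protocol. It is clearest for moderate depression and for the bilirubin, creatinine and ALT/AST rows, and partial for cytopenias. The discontinuation sentence in 4a5.2 also conflicts with Table 1 on stable moderate depression, and the 4a5.4 pointer leads to a definition that does not exist. These findings rest on the text alone.

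The effect on the SAE outcome and the stopping rule cannot be sized. The step 4 probabilities show only that the choice of definition could decide whether 10% is reached, under assumed rates and an unstated denominator. The missing denominator is a separate gap that would remain under any SAE definition. The point should be corrected before the safety data are classified.

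**What to change.** - **4a5.2.** Reconcile the trigger sentence and the discontinuation sentence with Tables 1 and 2 and with the table titles, so that it is clear what starts a dose change and what ends treatment.
- **7b.** Report two outcomes separately: (a) SAEs meeting 8c2, and (b) any AE or laboratory value leading to PEG dose change or discontinuation.
- **7d.** Name the SAE definition that the frequency counts, in wording consistent with the distinction drawn in 8c2.1.
- **4a5.4.** Reconcile the pointer on unacceptable toxicity with what 8c contains.

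Which clinical rule applies and what stops the trial remain the sponsor's decisions. The cost is protocol wording. One secondary outcome becomes two, and SAE counts may be smaller than under the loose usage.

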All subjects will complete screening, baseline, end-of treatment and post-treatment assessments. All of these assessments will take place in the YRG-JHU ICC in Bilaspur. Screening assessments will be completed within 28 days of the Baseline/Day 1 visit. Participants in all three arms will be asked to complete 4 study visits: 1) Screening; 2) the Baseline/Day 1 of treatment visit; 3) End of treatment visit (at 4 weeks for participants in Arm 1 and at 12 weeks for participants in Arms 2 and 3); and 4) 12 weeks post treatment completion visit (SVR12). In addition, subjects in Arm 1 will need to visit the clinic for an additional 3 visits to receive their PEG injections and participants in Arm 3 will need to come in at Weeks 4 and 8 for medication refills. Finally, subjects in Arms 1 and 2 will receive daily visits from field staff to receive their study medications.

The details of procedures at each visit are listed below. Information on laboratory parameters to be measured and details regarding the clinical assessments that will be performed are provided in 4a5.6.

4a3. Screening and Consent Procedures

Subjects will complete all screening assessments within 28 days of the Baseline/Day 1 visit. Written informed consent will be obtained from subjects prior to the assessment of study eligibility. Those who fail to satisfy eligibility criteria for the trial will still be able to receive services provided by the ICC. If they are still visiting the ICC, they will be allowed to re-screen for the pilot trial if they were excluded because of a modifiable exclusion criteria (e.g., Platelet count <50,000 cells/ml).

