- Obtain blood samples for laboratory tests listed in Table 3
- Brief survey on quality of life and alcohol and drug use
- Chart review of YRG-JHU ICC data to document HIV and antiretroviral therapy status and engagement in opioid substitution therapy (OST)

4a5.6. Additional details on laboratory tests and clinical assessments at visits.

Table 3. Schedule of assessments:

	Screening	Baseline/ Day 1	End of treatment****	SVR 12*****
HCV RNA	X			X
HIV*	X			
HBsAg*	X			
IL 28b		X		
Prothrombin time	X	X		
α fetoprotein	X			
TSH**	X			
CBC with diff**	X			X
LFT**	X			X
RFT**	X			X
Complete physical exam	X			
Targeted Physical Exam		X	X	
Sample Storage	X		X	X
Adherence assessment***			X	

*HIV and HBsAg will only be done if the subject has not been tested in the past 3 months

**TSH = Thyroid stimulating hormone; CBC = complete blood count; LFT = Liver function tests; RFT = Renal function tests

****at 5 weeks for Arm 1, 12 weeks for Arms 2 and 3

*****At 17 weeks for Arm 1, 24 weeks for Arms 2 and 3

HCV RNA will be assessed using the Abbott Realtime HCV assay and will quantify the number of copies of HCV RNA per milliliter (copies/ml). Complete blood count (CBC) will include hemoglobin, total white blood cell (WBC) count, total lymphocyte count, packed cell volume, total red blood cell (RBC) count, differential count, erythrocyte sedimentation rate, mean corpuscular volume, mean corpuscular hemoglobin, mean corpuscular hemoglobin concentration and platelet count. Liver function tests (LFT) will include ALT, AST, total and direct bilirubin, total protein, serum albumin, serum globulin, albumin-globulin ratio, γ-GT and alkaline phosphatase.

Renal function tests

(RFT) will include blood urea nitrogen and serum creatinine. Plasma will be processed and stored at -70° C for future testing.

Complete physical examination: A complete physical examination will include documentation of general appearance and examination of the following body systems: head, neck and thyroid; eyes, ears, nose, throat, mouth and tongue; chest (excluding breasts); respiratory; cardiovascular; lymph nodes, abdomen; skin, hair, nails; musculoskeletal; neurological.

Targeted physical examination: This exam will focus on signs and symptoms related to liver disease.

Retinal examination: A fundoscopic retinal examination will be performed for those in Arm 1. This will be performed by the study doctor and the subject may be referred to a specialist if needed.

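### Table 2 makes interferon dosing depend on laboratory values, but no blood count, liver or renal panel is scheduled between Screening and SVR12 for Arm 1 participants who do not stop early

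*Combined protocol and SAP*

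**What the plan says.** **The dose rule.** Section 4a5.2 gives "Table 2. Procedures for Dose modification for serious adverse events related to hematologic abnormalities". In Arm 1, PEG is halved or stopped for good when hemoglobin, white cells, neutrophils, platelets, bilirubin, creatinine or ALT/AST pass printed limits. The lead-in ties modification to a serious reaction arising on treatment and refers to standard guidelines that are not reproduced. The first injection belongs to Day 1. For the rest, section 4a2 says that "subjects in Arm 1 will need to visit the clinic for an additional 3 visits to receive their PEG injections".

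**The tests.** These are set out in section 4a5.6, "Table 3. Schedule of assessments". The CBC, LFT and RFT rows are marked under Screening and SVR12 only. On the first of these, section 4a2 states: "Screening assessments will be completed within 28 days of the Baseline/Day 1 visit". The Day 1 blood tests are IL28b and prothrombin time. The table has no column for the later PEG visits. At End of Treatment the instruction in section 4a5.3 is "Obtain blood samples for sample storage in Table 3", and section 4a5.6 adds "Plasma will be processed and stored". The only other listed CBC, LFT and RFT are in section 4a5.4: "Subjects discontinuing treatment prior to completion of the assigned dosing period will be asked to complete an Early Termination visit".

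**The outcome.** Section 7b says: "Serious adverse events requiring dose modification or treatment discontinuation will include primarily laboratory abnormalities including anemia, neutropenia and thrombocytopenia".

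**The concern.** A dose rule can work only if the quantity it depends on is measured in time. Every Table 2 trigger is a laboratory value, and a low neutrophil or platelet count or a raised ALT may cause no symptoms. The side-effect questions at weekly and daily visits (section 8b) need not prompt a test. A participant could then receive the next PEG dose with a Table 2 limit already crossed and nobody aware of it. Table 1, the depression table in the same section, shows the contrast: it pairs its dose actions with a surveillance schedule or an immediate consultation. Table 2 has no such counterpart.

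The safety data are also affected. Section 7b expects events that change or end treatment to be mainly anemia, neutropenia and thrombocytopenia, and all three need a CBC. Among participants who finish treatment, such an event is recorded only if someone orders an unscheduled test.

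**Working it through.** The plan gives no figure of its own on laboratory monitoring to reproduce, and its power statement in section 7c does not depend on this point. The check compares Table 2 with every visit that lists a blood test, then does the timing arithmetic.

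**Step 1: listed CBC, LFT and RFT in Arm 1.**
- Screening: yes (Table 3).
- Baseline/Day 1: no. IL28b and prothrombin time only.
- PEG visits 2 to 4: none named (sections 4a2, 4a5.2; no Table 3 column).
- End of Treatment: no. Storage only, according to both Table 3 and the text of 4a5.3. That agreement makes a lost table mark an unlikely explanation. The stored material is plasma, so a CBC cannot be run on it later.
- Early Termination: yes, but only after treatment has been discontinued.
- SVR12: yes (Table 3).

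Scheduled panels from Day 1 to End of Treatment for a participant who does not stop early: 0.

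**Step 2: how much of Table 2 needs a CBC.** Printed actions: hemoglobin 1, white cells 2, neutrophils 2, platelets 2, so 1 + 2 + 2 + 2 = 7. The bilirubin rows are damaged in the available text, so nothing here rests on them.

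**Step 3: age of the newest scheduled value.** Assume an uninterrupted weekly course with injections on Days 1, 8, 15 and 22, and Screening at the limit of 28 days before Day 1.
- Injection 2: 28 + 7 = 35 days.
- Injection 3: 28 + 14 = 42 days.
- Injection 4: 28 + 21 = 49 days.

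These are upper values for that course. A later Screening date shortens them. The extensions and restarts allowed in section 4a5.2 lengthen them. In every case the value predates the first PEG dose.

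**Step 4: how late the next scheduled panel is.** SVR12 in Arm 1 is Week 16 in the 4a5.5 heading and Week 17 in the Table 3 footnote.
- Study day: 16 × 7 + 1 = 113, or 17 × 7 + 1 = 120.
- Days after the last injection: 113 − 22 = 91, or 120 − 22 = 98.
- In PEG half-lives of 80 hours (section 6a3): 91 × 24 / 80 = 27.3, or 98 × 24 / 80 = 29.4. Drug half-life is not blood-count recovery time, which the documents do not give. The figure shows only that this panel is remote from exposure.
- Longest gap between scheduled panels in an uninterrupted course: 28 + 112 = 140 days, or 28 + 119 = 147 days.

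**Step 5: dosing occasions affected, and the effect of the fix.** Arm 1 has 50 participants and three later injections each: 50 × 3 = 150 occasions. This unit is mine. The protocol does not itself require a check at each injection.
- Now: 0 of 150 have a scheduled value taken after PEG began.
- With panels at Day 1 and at each PEG visit, and same-day results: 150 of 150.
- With results available one visit later: injections 3 and 4 rest on the Day 8 and Day 15 samples, so 50 × 2 = 100 of 150. Injection 2 rests on the Day 1 sample, 7 days old instead of up to 35.

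**The case against.** Several objections have force.

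- **Other cover exists.** Unscheduled tests are not forbidden, section 4a5.4 allows stopping on clinical judgment, section 4a5.2 cites standard guidelines, and section 9a promises monitoring that includes blood tests. This stands as mitigation. None of these names a test or a time, so none supplies the missing measurement.
- **Table 3 is not exhaustive.** It covers only the four visits common to all arms and omits, for example, the Early Termination tests. Its silence on PEG visits is therefore weaker evidence than it first appears. But no other section names a laboratory test at those visits either.
- **Entry limits leave room.** Section 5 requires neutrophils of at least 1,500/µL and platelets of at least 90,000/µL, against reduction limits of 750 and 50,000. The hemoglobin margin is narrow for women: 9 g/dl at entry against a stop below 8.5. The prior pilot reported no serious events in its arm with 12 weeks of PEG and no discontinuations for side effects. This suggests few serious events, but gives no rate of threshold crossings.

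A reader might go further and infer that section 7b has no laboratory data at all, that the comparison between arms is biased, or that the 10% stopping rule in section 7d is disabled. The documents do not support these. Early discontinuers do get a panel. Section 7b concerns serious events, which section 8c2 defines by outcome rather than by every threshold crossed. The direction of any imbalance is unknown, because Arm 1 also has the most clinic contact at which extra tests might be ordered.

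**Conclusion.** The point holds for Arm 1 participants who do not stop early. Followed as written, the protocol has a laboratory-based dose rule with no scheduled laboratory result able to activate it before injections 2 to 4. This touches all 150 later dosing occasions if every Arm 1 participant completes. The newest scheduled value may be up to 35, 42 and 49 days old and is always from before PEG. Laboratory events requiring dose modification are captured only through unscheduled tests or, in those who stop, through the Early Termination panel.

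The timing assumes weekly injections from Day 1 without interruption and the longest permitted Screening interval. The count of zero scheduled panels depends on neither assumption. How many crossings would be missed cannot be estimated from the documents, and the number may be small. This should be corrected because a stated safety rule lacks its measurement and the remedy is inexpensive. It does not bear on the SVR12 analysis or on the stated power.

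**What to change.** 1. **Table 3 and section 4a5.1:** add CBC with differential, LFT and RFT at Baseline/Day 1, using the draw already scheduled. This also gives the ALT/AST rule, which compares with baseline, a current reference value.
2. **Table 3:** add an Arm 1 column with the same panels at each later PEG injection visit. Define it by visit rather than by fixed day, so that extended and restarted courses are covered.
3. **Section 4a5.2:** add *The most recent results will be checked against Table 2 before each injection; if same-day results are not feasible, each sample governs the next injection.*
4. **Optional:** add the panel at the existing End of Treatment draw in all arms as a descriptive safety reading. State that the visit falls at Week 4 to 5 in Arm 1 and Week 12 in Arms 2 and 3. Do not define a new between-arm outcome from it.

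**Cost.** The PEG visits need up to 50 × 3 = 150 panels, each with a new blood draw at an existing visit, and more if courses are extended or restarted. Day 1 needs extra tubes. Because section 4a5.1 places that draw before randomization, this means up to 150 participants. The optional step adds up to 150 panels at a draw already planned. No new visits, participants or assays are required. Same-day turnaround at the site is not documented, which is why the lagged rule is included. Under that rule the sample from the last PEG visit governs no injection and serves only as a safety reading. Testing becomes more intensive in Arm 1 than in the other arms, so PEG-visit findings should be reported descriptively.
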